19.5. PHYSICAL EXAMINATION

Physical examination dates and reason that an examination was not done will be presented in data listings. Any clinically significant findings for physical examination are recorded as adverse events.

19.6. VITAL SIGNS

The following vital signs measurements will be reported for this study:

- Systolic Blood Pressure (mmHg)
- Diastolic Blood Pressure (mmHg)
- Pulse Rate (bpm)
- Temperature (°C)
- Weight (kg)
- Height or length (cm)
- Head circumference (cm) for subjects \leq 36 months of age

The following vital signs parameters will be derived for this study:

- BMI (kg/m²)
- Height Z-score
- Weight Z-score
- BMI Z-score

Document: \\quintiles.net\Enterprise\Apps\sasdata\SASa\sas\Shire\Teduglutide\Biostatistics\Documentation\SAP\TE
D-C14-006_SAP_Final_V1.0_20170714

Author: PPD Version Number: Final V1.0
Version Date: 14Jul2017

Template No: CS_TP_BS016 – Revision 3
Effective Date: 01May2012

Reference: CS_WI_BS005

Copyright © 2012 Quintiles Transnational Corp. All rights reserved.

The contents of this document are confidential and proprietary to Quintiles Transnational Corp. Unauthorized use, disclosure or reproduction is strictly prohibited.

- Head circumference Z-score for subjects ≤ 36 months of age

Descriptive statistics will be used to summarize vital signs measurements and derived parameters in actual value and change from baseline for each treatment group by age group (age stratification used for randomization: <1 year, 1-<12 years, 12-<17 years and 17-<18 years and overall) at study site visits (including EOT) where associated parameters are collected. Z-scores of vital signs by site visits will be presented in box plots. A listing will also be provided.

19.6.1. VITAL SIGNS SPECIFIC DERIVATIONS

- BMI

$BMI = 10000 * \text{Body weight (kg)} / \text{body height (cm)}^2$, where both body weight and body height data are available at the same scheduled visit

- Height, Weight, Head Circumference and BMI Z-scores

Official and validated SAS programs created by Centers for Disease Control and Prevention (CDC) will be used to calculate the Z-scores (standard deviations) for a child's sex and age (up to 20 years of age) for BMI, weight, height, and head circumference based on the CDC growth charts for children age 2 years and older and the WHO growth charts for infants and children < 2 years of age. For more information on the CDC SAS programs, see http://www.cdc.gov/growthcharts/computer_programs.htm.

Z-scores are calculated as the formula below:

$$Z\text{-score} = [((\text{observed value} / M) ^ L) - 1] / (S * L)$$

In which 'observed value' is the child's height, weight, head circumference or derived BMI. The L, M, and S values vary according to the child's sex and age. For more information on the LMS method, see <http://www.ncbi.nlm.nih.gov/pmc/articles/PMC27365/>.

19.7. ECG EVALUATIONS

Electrocardiogram (ECG) results with description of any findings will be recorded in the eCRF. The following ECG parameters will be reported for this study:

- Overall assessment of ECG (Investigator's judgment):
 - o Normal
 - o Abnormal, Not Clinically Significant (ANCS)

Document:	\\quintiles.net\Enterprise\Apps\sasdata\SASa\sas\Shire\Teduglutide\Biostatistics\Documentation\SAP\TE D-C14-006_SAP_Final_V1.0_20170714		
Author:	PPD	Version Number:	Final V1.0
		Version Date:	14Jul2017
Template No:	CS_TP_BS016 – Revision 3	Reference:	CS_WI_BS005
Effective Date:	01May2012		

- o Abnormal, Clinically Significant (ACS)

The following summaries will be provided for ECG data by treatment group at baseline, week 12, week 24 and EOT:

- Incidence of Normal, ANCS and ACS
- Listing of all ECG descriptions for subjects meeting ACS criteria

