6.1.9 Electrocardiograms

Twelve-lead electrocardiograms will be performed according to the Schedules of Evaluations and Procedures ([Table 6-1](#) and [Table 6-2](#); [Table 6-3](#) and [Table 6-4](#) for the standard of care group). The ECG tracing will be read by a local experienced physician. Results (normal, abnormal not clinically significant, and abnormal clinically significant with description of the finding) will be recorded on the eCRFs.

Any clinically significant changes from baseline (in the opinion of the investigator) noted during the ECG evaluations should be recorded on the appropriate AE page of the eCRF. This will assist the sponsor/designee in collecting additional information about that abnormality, including information regarding relationship to study drug or other causes, any action taken, and outcome.

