8.2 Safety and Tolerability Variables

The safety and tolerability variables include:

- Adverse events, including GI symptoms
- Physical examination
- Vital signs, including temperature, heart rate, blood pressure, body weight, head circumference (up to 36 months of age), height or length, and trends on growth charts
- Electrocardiograms
- Laboratory safety data, including clinical chemistries, hematology and urinalysis
- Change in urine output (collected or calculated volume)
- Fecal output (by volume or number of bowel movements per day)
- Antibodies to teduglutide (active treatment group only)
- GI-specific testing (active treatment groups only) including colonoscopy or sigmoidoscopy, abdominal ultrasound, fecal occult blood testing, UGI/SBFT

Adverse events will be coded using the current version of MedDRA. Treatment emergent AEs will be summarized by system organ class and preferred term for each treatment group. The number and percentage of subjects with AEs, SAEs, AEs that lead to discontinuation, study drug-related AEs (determined by the investigator), and AEs that lead to death will be summarized by treatment group. AEs will also be summarized by treatment group with regard to intensity and relationship to study drug. For AEs of special interest, the CTCAE grading system will be used as described in Section 6.1.4.

For laboratory tests, vital signs, body weight, ECG, and fluid balance variables, descriptive statistics (mean, median, standard deviation, minimum and maximum values, the number and percentage of subjects in specified categories) will be calculated to summarize the absolute values and change from baseline at each scheduled visit for each treatment group.

The number and percentage of subjects classified as having positive specific antibodies to teduglutide will be used to summarize the presence of antibodies for each treatment group.

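### The planned ECG tables cannot count children who became abnormal relative to baseline, and they leave out the Week 28 post-treatment ECG

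*SAP*

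**What the plan says.** Protocol 8.2 includes ECG in its general sentence on safety summaries: "For laboratory tests, vital signs, body weight, ECG, and fluid balance variables, descriptive statistics" "will be calculated to summarize the absolute values and change from baseline at each scheduled visit for each treatment group". The statistics it names include counts and percentages in categories as well as means. The safety paragraph of the protocol synopsis also has ECG data summarised by visit and time point.

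Protocol 6.1.9 fixes the scale: "Results (normal, abnormal not clinically significant, and abnormal clinically significant with description of the finding) will be recorded on the eCRFs". No numeric intervals are recorded.

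Protocol Tables 6-1 and 6-2 schedule ECGs at Screening, Week 12, Week 24 (or EOT/ET) and Week 28 (or EOS) in the active groups. Tables 6-3 and 6-4 give the same times for standard of care.

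SAP 19.7 sets the outputs: "The following summaries will be provided for ECG data by treatment group at baseline, week 12, week 24 and EOT". Two items follow: "Incidence of Normal, ANCS and ACS" and "Listing of all ECG descriptions for subjects meeting ACS criteria". There is no shift or change from baseline for ECG, and no Week 28/EOS time point.

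**The concern.** Separate counts at separate visits show how many children are in each category at a visit, but not who moved. A safety reader wants to know how many children with a normal tracing at baseline had an abnormal one on each dose, and whether it resolved after the drug was stopped. The tables in SAP 19.7 answer neither question.

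ECG is also the exception within the SAP. Laboratory data get change from baseline and a shift by normal range (SAP 19.2). Vital signs and weight get change from baseline (SAP 19.6), and so do urine and fecal output (SAP 19.8). Only ECG loses the baseline comparison that Protocol 8.2 asks of all of them.

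The arms are small, with a minimum of 10 subjects per dose (Protocol 4.1), so one or two new abnormalities change the picture.

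**Working it through.** The plan states no figure to reproduce. The check compares the schedule with the outputs, and then asks what the planned table can identify.

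**1. Scheduled ECGs against tabulated ECGs**

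| Time | Scheduled in supplied protocol | Tabulated in SAP 19.7 |
|---|---|---|
| Screening (serves as baseline under SAP 7.2) | yes | yes |
| Week 12 | yes | yes |
| Week 24/EOT | yes | yes |
| Week 28/EOS | yes | no |

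Three ECGs are scheduled after baseline and two are tabulated, so 1/3 = 33% is left out. The separate EOT time point does not recover it: SAP 7.4 takes EOT from the last measurement within the 24-week treatment period, and Week 28 comes after that.

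**2. What change from baseline means here**

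The result is a three-level category, so change from baseline can only mean a change of category. A cross-tabulation of baseline category against later category shows it. A list of counts per visit does not.

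**3. What the planned counts identify**

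Let N be the subjects in an arm with both readings, a the number non-normal at baseline, and b the number non-normal later. The number newly non-normal lies between max(0, b − a) and min(b, N − a).

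Take N = 10, the protocol minimum per dose arm. The values of a and b are assumptions, since the documents give no ECG abnormality rates.

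| a (baseline) | b (later) | Lower: max(0, b − a) | Upper: min(b, 10 − a) |
|---|---|---|---|
| 1 | 1 | 0 | 1 |
| 2 | 2 | 0 | 2 |
| 3 | 3 | 0 | 3 |
| 3 | 2 | 0 | 2 |
| 2 | 3 | 1 | 3 |

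In the third row, 10 − 3 = 7 children are normal at baseline, so the same table fits a new-abnormality rate from 0/7 = 0% to 3/7 = 43%. A shift table would give the exact number in every row.

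**4. What other outputs recover**

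- *Adverse events.* Under Protocol 6.1.9, clinically significant changes from baseline "noted during the ECG evaluations should be recorded on the appropriate AE page of the eCRF". Protocol 6.1.1.2 collects AEs through the last study visit, and SAP 19.1 puts no end date on treatment emergence. A significant change at Week 28 should therefore reach the AE tables.
- *ECG listing.* Subjects with an ACS reading have their descriptions listed, so their baseline and later findings can be compared. The listing sits under the sentence that names the four time points, so it is unclear whether Week 28 is included.
- *General listing rules.* SAP 7.3 says that listings cover scheduled and unscheduled data. SAP 20 sends collected data not described elsewhere to appendix listings, but ECG is described in 19.7, so neither rule clearly commits to listing every ECG of subjects without an ACS reading.

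That leaves Normal-to-ANCS shifts, the return of an ANCS or ACS reading to normal after treatment, and any count of shifts by dose group.

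**The case against.** The strongest defence starts from the protocol synopsis, which plans differences from baseline for quantitative safety data where applicable and frequency counts for qualitative data. ECG is qualitative, so incidence by category is arguably what was planned, and Protocol 8.2 is one generic sentence that never mentions a shift table. Clinically significant changes reach the AE tables in any case, and with about 10 children per arm a reader can trace the rest by hand. The residue is changes that the investigator judged not clinically significant.

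Part of this stands. A shift table is not named in the protocol, and clinically important events are not lost. But Protocol 8.2 does name ECG for change from baseline and allows for categorical results, and the synopsis wording does not explain why Week 28 is left out. Reading by hand works only if every ECG is listed, which SAP 19.7 does not promise; the output shells are in a separate file that was not supplied.

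A reader might also draw three stronger conclusions that the documents do not support.

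- *That Week 28 is the only ECG off drug, or that every off-drug ECG is left out.* The screening ECG precedes dosing and is tabulated as baseline. All standard-of-care ECGs are off teduglutide, and those up to Week 24 are tabulated. Week 28 is the only post-treatment ECG.
- *That SAP 4.3 is wrong to declare no change from protocol.* SAP 2 says that the SAP follows Amendment 4 of 15 March 2016. The supplied protocol ends at Amendment 2 of 06 October 2015, and the versions visibly differ, for example in schedule table numbers, visit windows and age stratification. Amendment 4's ECG schedule and analysis wording cannot be checked here.
- *That the gap would hide heart failure.* Protocol 6.1.4 lists heart failure as an identified risk but grades it by symptoms and intervention, which AE reporting captures directly.

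**Conclusion.** The point holds as a minor gap in safety reporting. As written, SAP 19.7 cannot give the number of children newly abnormal relative to baseline in any group, and it omits 1 of the 3 scheduled post-baseline ECGs from its summary. No efficacy result, sample size or hypothesis test is affected.

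The identifiability gap follows from SAP 19.7 alone, whatever the protocol version. The Week 28 omission assumes that Amendment 4 kept the Week 28 ECG of the supplied protocol. The range of 0 to 3 newly abnormal children illustrates the ambiguity for assumed counts in an arm of 10; it is not a forecast.

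**What to change.** In SAP 19.7:

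1. Add Week 28/EOS to the summary time points, after checking the Amendment 4 ECG schedule.
2. Add a shift table for each dose group and standard of care: baseline category (Normal, ANCS, ACS) by worst on-treatment category, and by Week 28/EOS category. For standard of care, the worst category is taken over the same 24 weeks.
3. List all ECG results with descriptions for all subjects, rather than only for those with an ACS reading.

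If Week 28 or the baseline comparison was left out on purpose, state the reason in the SAP.

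The cost is one more time point, one shift table and a wider listing. All of it uses data that the supplied protocol already collects, with no added visit or procedure.

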19.8. FECAL AND URINE OUTPUT

Urine and stool output data is recorded over a 48 hour period of PN/IV and EN stability before every scheduled site visit and within 1 week of implementing any PN/IV prescription adjustment.

The average daily urine output (mL/kg/day) at the scheduled site visit will be calculated as follows:

$(\text{Total urine output over 48 hours} / 2) / \text{body weight (kg) at the scheduled visit}$

where total urine output is calculated as the sum of the urine output in mL and the urine-only diaper weights in g (1g = 1mL) for the subject collected on the output diary form of eCRF. Values will not be calculated if the urine output is not available at the visit. If the body weight at the scheduled visit is missing, the last available weight assessment will be used.

The average daily fecal output will be summarized separately by the average number of stools per day, the average typical stool form score using Bristol Stool Form Scale, the average total daily stool/mixed stool diaper weight (g/kg/day) and the average ostomy output per day (mL/kg/day) for each visit. The average number of stools per day and the average typical stool form score will be calculated as (sum of the daily data in a 48-hour period / 2). The body weight will be used to calculate the daily stool/mixed stool diaper weight (g/kg/day) and the total ostomy output per day (mL/kg/day) using the same formula as we use for calculate the average daily urine output.

The change and the percent change in average daily output for stool and urine from baseline to each scheduled visit, as well as at EOT, will be presented by treatment group using descriptive statistics. The change and the percent change in average daily output for fecal and urine output from baseline to each scheduled visit, as well as at EOT, will be presented by treatment group using descriptive statistics. A listing will also be provided.

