6.1.13 Diaries

Subjects or subjects' parent or guardian will be required to complete the following:

- Intake Diaries, completed daily, which will include:
 - PN/IV volume and calories (days per week, hours per day)
 - EN (formula and specialized electrolyte solutions) volume and calories (days per week, hours per day)
 - Other Nutrition (regular diet and drink) intake (to be converted into calories by site personnel)
- Urine/Stool Output Diary, completed for 2 days (48 hours) just prior to every scheduled clinic visit and telephone contact, consisting of :
 - Collection of urine data:
 - For those who are toilet trained and NOT IN DIAPERS: All urine output should be measured and recorded in mL. The subject or parent will perform dipstick specific gravity tests on the first urine produced after the daily infusions of PN/IV support.
 - For those who are not toilet trained and IN DIAPERS: The weight of all urine-only diapers will be recorded. Volume will be calculated based on the formula: 1g (scale weight) = 1 mL or 1 cc. At the discretion of the investigator, the parent may be asked to collect the first void after the daily infusion of PN/IV support to measure the specific gravity.
 - Collection of stool output data (including stool only and mixed urine/stool diapers):
 - For those who are toilet trained and NOT IN DIAPERS: Daily stool count will be recorded.
 - For those who are not toilet trained and IN DIAPERS: The weight of all diapers that contain stool (including diapers that contain mixed stool and urine) will be recorded as stool output. Stool volume will be calculated based on the formula: 1 g (scale weight = 1 mL or 1 cc).
 - All ostomy output will be recorded as stool output and measured in cc or mL.
 - In addition all subjects (toilet trained or not) will report on the average consistency (form) of the stool passed each day during the 48-hour

period. The subject or parent will use the Bristol Stool Form Scale (Lewis and Heaton, 1997) to make the assessment.

During the screening period, these diaries focusing on Intake and Output will be completed every day.

All diaries will be reviewed by the investigator or their designee at each visit or telephone contact to assess clinical status and opportunity for PN/IV changes and advance in feeds. At each visit, the diaries will be reviewed for completeness and accuracy of the data.

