17.1. PRIMARY EFFICACY

17.1.1. PRIMARY EFFICACY VARIABLE & DERIVATION

The primary efficacy variable is weight-normalized reduction in PN/IV volume of at least 20% at EOT compared to baseline. This will be analyzed in two ways: 1) based on the subject diary data (also referred to as “actual”), and 2) based on the investigator-prescribed data (referred to as “prescribed”). PN/IV support will be reported in both subject diary data and the investigator-prescribed data in the eCRF. Investigator-prescribed data are the most recent PN/IV prescription (from either baseline or prescription adjustments) prior to or on the date of visit, captured in the PN/IV history and PN/IV adjustments eCRFs. PN/IV diary data are collected over 24-hour periods that start on the assigned date. Depending on the time of day at which the 24 hour period begins, which can vary by subject, overnight PN/IV infusion volumes after midnight may be associated with prior the date. Baseline actual PN/IV parameters will be calculated using all the diary data collected within 14 days prior to the first dose or baseline visit. Calculation of post-baseline actual PN/IV parameters will be based on the daily support recorded in subjects’ diaries within 7 days prior to the date of each scheduled post-baseline visit. Week 1 calculations will exclude any pre-baseline diary data. The calculation of actual PN/IV volume normalized to weight will follow the formula below:

$$\text{Average daily value} = [(\text{sum of non-missing daily values in the diary} / \text{number of days with non-missing values})] / \text{last available body weight prior to the visit}$$

If more than 2 days’ values in a week are missing, the average daily value will not be calculated and will be assigned as missing. The same strategy will be used to calculate all other average diary parameters, including PN/IV calories, PN/IV hours per day, EN volume, and EN calories. If more than 5 days’ values in two weeks before baseline visit, the baseline values are missing.

The calculation of prescribed PN/IV volume normalized to weight will follow the formula below:

$$\text{Average daily value} = (\text{prescribed weekly PN/IV volume} / 7) / \text{last available weight prior to or on the date of visit}$$

An analogous strategy will be used to calculate other prescribed parameters, including PN/IV calories, PN/IV hours per day, EN volume, and EN calories.

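### SAP 19.8 divides every 48-hour output measure by a fixed 2 and does not say what to do when only one of the two days was recorded

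*SAP*

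**What the plan says.** Protocol 6.1.13 asks families for a "Urine/Stool Output Diary, completed for 2 days (48 hours) just prior to every scheduled clinic visit and telephone contact". SAP 19.8 then defines the daily averages:

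- **Urine:** the 48-hour total is divided by 2 and then by body weight.
- **Stool count and stool form score:** each "will be calculated as (sum of the daily data in a 48-hour period / 2".
- **Stool or mixed diaper weight, and ostomy volume:** derived "using the same formula as we use for calculate the average daily urine output".

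The one availability rule in the section is "Values will not be calculated if the urine output is not available at the visit". It names urine only. No counterpart is given for the fecal measures, and a window with one recorded and one blank day is not mentioned.

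The section then reports, by treatment group, "The change and the percent change in average daily output for stool and urine from baseline to each scheduled visit, as well as at EOT".

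SAP 17.1.1 treats the intake diaries differently. The numerator is the "sum of non-missing daily values in the diary", the divisor is the count of days that have a value, and a limit on missing days decides when the average is set to missing. SAP 8.3 and protocol 8.6.2 give the general position: missing data are as a rule not imputed, and missing safety parameters are not imputed.

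**The concern.** A divisor of 2 is right only if both days are present. If one day is blank and the recorded day is still divided by 2, the blank day has in effect been entered as zero output. That is an imputation the plan elsewhere says it will not make.

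The error has a direction. A blank day after baseline lowers the reported output, which for stool or ostomy volume looks like benefit and for urine looks like fluid loss. A blank day in the baseline window does the opposite. Protocol 8.2 lists both urine and fecal output as safety variables, and protocol 8.3 lists fecal output again as a pharmacodynamic variable. SAP 7.4 defines EOT as the last available measurement in the treatment period, so a half-recorded window could also become the EOT value. The analysis is purely descriptive and each arm has about 10 children, so the tabulated means and changes are what a reader will rely on.

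**Working it through.** The plan states no figure on this point, so there is none to reproduce. The check applies the SAP 19.8 formula literally and compares it with a divisor equal to the number of recorded days.

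**Inputs.** Fixed divisor of 2 (SAP 19.8); percent change as (visit - baseline) / baseline x 100 (SAP 7.6); at least 10 subjects per arm (protocol 4.1). Illustrative assumption: 600 mL per day and 15 kg. The percentages do not depend on these two values as long as output and weight are unchanged.

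**One child, volume measure, equal output on both days**

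| Baseline window | Visit window | Baseline value (mL/kg/day) | Visit value (mL/kg/day) | Apparent change |
|---|---|---|---|---|
| both days | both days | (600+600)/2/15 = 40 | 40 | 0% |
| both days | one day | 40 | 600/2/15 = 20 | (20-40)/40 = -50% |
| one day | both days | 20 | 40 | (40-20)/20 = +100% |
| one day | one day | 20 | 20 | 0% |

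Dividing by recorded days gives 600/1/15 = 40 mL/kg/day for every one-day window, so all four rows show 0%.

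**Counts and scores.** Eight stools on the one recorded day become 8/2 = 4 per day. A stool form score of 6 becomes 6/2 = 3, a different stool type, although the only recorded score was 6.

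**When output has really changed** (complete baseline, one day recorded at the visit). The literal result is (1 + true change)/2 - 1. A true rise of 20% shows as 1.2/2 - 1 = -40%. A true fall of 20% shows as 0.8/2 - 1 = -60%.

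**When the two days are unequal.** Keep the true 48-hour total unchanged and let the recorded day hold a share s of it. The literal formula gives an apparent change of s - 1: -70% at s = 0.3 and -30% at s = 0.7. Dividing by recorded days gives 2s - 1: -40% and +40%. The second is noisy but centred on zero; the first is centred on -50%.

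**Arm mean.** With 10 contributing children and unchanged output, k children with a blank day at the visit shift the mean percent change by -50k/10: -5, -10 and -15 points for k = 1, 2 and 3. A child whose baseline window is the incomplete one shifts it by +100/10 = +10 points.

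**The case against.** **The volumes and weights can be read differently.** The urine numerator is a total over 48 hours. With one blank day no such total exists, so a programmer could treat the output as not available and leave the value missing. Diaper weight and ostomy volume borrow the same formula. That reading also fits SAP 8.3 and protocol 8.6.2 better. SAP 17.1.1 further extends its approach to other averaged diary quantities, and its list, which names only PN/IV and EN items, need not be exhaustive. This stands in part. A reader might infer that halving is certain for every measure, and the text does not support that. The text also does not rule halving out: 19.8 gives its own fixed divisor, and for stool count and form score the numerator is simply the sum of the daily data.

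**Frequency is unknown.** A reader might assume a missing-day rate and project how many windows and how much of the arm mean are affected. The documents give no such rate and no ground for treating consecutive days as independent. They describe controls that should limit gaps: diary review at each visit or contact (protocol 6.1.13), and full source verification and queries (protocol 7.1). This objection stands.

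**Not every child contributes to every fecal measure.** Under protocol 6.1.13, toilet-trained children have counts, children in diapers have weights and children with an ostomy have volumes. The 10-child arithmetic therefore applies only where all 10 contribute. With m contributors the shift per affected child is -50/m points, larger when m is below 10.

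**Consequences are bounded.** The PN/IV endpoint has its own derivation. No significance claims are made (SAP 7.5), medians accompany means, a listing is provided, and investigators work from the diaries themselves. All true, and it limits the weight of the point without removing the error.

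**Conclusion.** The point holds as a gap that, on a literal reading, yields a wrong value. The fixed divisor covers five output measures, no rule covers a one-day window, and the literal result counts the blank day as zero against the plan's own no-imputation rules. It is clearest for stool count and form score, and one of two readings for urine, diaper weight and ostomy volume.

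The figures of -50% (blank day at the visit) and +100% (blank day at baseline) assume unchanged output and weight, equal output on the two days, and the other window complete. A reader might take -50% as the general effect, but size and sign depend on which window is incomplete and how output is split between the days. The shift of about -5 points per affected child assumes 10 contributors. How often it would occur cannot be settled from the documents, and the primary PN/IV endpoint is unaffected. This is worth correcting because it can distort safety and supportive summaries in small arms; it does not threaten the main result.

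**What to change.** In SAP 19.8, replace the divisor of 2 with the number of 24-hour periods actually recorded in the window, for urine, stool count, stool form score, diaper weight and ostomy volume, at baseline and at every later time point including EOT. Set the value to missing if no day was recorded. The non-missing-day divisor can be referenced to SAP 17.1.1.

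SAP 17.1.1 should not be cited for keeping one-day windows. It sets an average to missing above 2 of 7 days (2/7 = 29%) or above 5 of 14 baseline days (5/14 = 36%), and one blank day in two is 50%. Setting one-day windows to missing is therefore an acceptable alternative, closer to those limits. Either removes the artefact; the SAP has to state one.

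The cost is one sentence and a small programming change. Under the first option some values rest on a single day and are noisier; under the second a few visit values are lost.
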